**Statistical Plan**

Data are presented as mean  $\pm$  standard error of the mean (SEM) and a significance was set a priori at  $P < 0.05$ . Normality was confirmed by the D'Agostino and Pearson test. A two-way ANOVA (Treatment Group x Time) with repeated measures for time was performed. Upon a significant effect, a Holm-Sidak's post-hoc test was used for multiple comparisons. When comparing the change ( $\Delta$ ) from pre to post-intervention between groups, data were analyzed using an unpaired t-test. Pearson's correlation coefficient ( $r$ ) was used to determine associations between dependent variables. GraphPad Prism 7.0 was used to perform statistical analysis

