**1. Purpose of the study**

- a) Provide a brief lay summary of the project in <200 words. The lay summary should be readily understandable to the general public, and is, for example, what would be released to a newspaper if requested.

We propose that post-exercise milk protein feeding will enhance the mitochondrial protein synthesis (biogenesis) response to an exercise-training program. In addition, we propose that this stimulatory effect of protein feeding will overcome the potential blunting effect of metformin on exercise responses. We will investigate these outcomes over a 12-week exercise-training program in older adults with pre-diabetes with or without metformin treatment.

Sub-study:

- 1. CGM in Individuals with prediabetes undergoing an exercise-training program with or without Metformin.
- 2. CGM in healthy control individuals to compare to individuals with prediabetes.

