**c) Proposed Start Date (may not precede IRB approval date):**

August 1, 2015

2.

Study Procedures (If this is a student project, the methods section of the thesis or dissertation proposal must be attached in section #16 - Attachment section.)

**a) In lay language, describe all the procedures, from screening through end-of-study, that the human subject must undergo in the research project, including study visits, drug treatments, randomization and the procedures that are part of standard of care. Please note: Do NOT respond "See Attachment Section." If you would like to add tables, charts, etc., attach those files in the Attachment section (#16).**

Study Overview:

Pre-diabetic and healthy participants will first undergo a medical questionnaire, resting ECG, graded exercise test with ECG and assessment of VO2max, anthropometric measurement (height, weight and body composition by DEXA scanning), an oral glucose tolerance test (OGTT), and a muscle biopsy.

Prediabetic participants will be screened to eliminate those lactose intolerant, medications known to affect the primary outcomes, medications or recent procedures contraindicated with metformin or not pre-diabetic. Subjects who meet these criteria will be randomized so that subject characteristics are matched between groups, while the study team and participants will remain blinded to treatment (i.e., randomized, double-blind study design). Subjects will be assigned to exercise + carbohydrate + placebo, exercise + protein + placebo, exercise + carbohydrate + metformin, or exercise + protein + metformin.

A minimum of two days apart from the VO2max test, skeletal muscle will be sampled from pre-diabetic and healthy participants. During these visits, pre-diabetic subjects will have the option to participate in a study to test the impact of one counseling session on physical activity after completion of the exercise training and to identify individual, socio-cultural and environmental determinants of physical activity 12 weeks after the end of the exercise intervention. If the subjects wish to participate they will complete questionnaires to measure sociodemographic information, physical activity, self-efficacy, planning, self-regulation and outcome expectancy of exercise, and perceptions of neighborhood support at baseline, completion of exercise training and 12 weeks after the exercise training.

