Pre diabetic and healthy participants will also have the option to participate in a study to wear a Dexcom generation 6 (G6) continuous glucose monitor (CGM) to measure glucose values every 5 minutes. Healthy participants will wear the device once for up to 10 consecutive days. Pre-diabetic participants will wear the device for up to 10-consecutive days at three different time points: before, during and after the 12-week exercise intervention for a total of 30 days wearing the CGM. The Dexcom G6 CGM is for investigational use only and is not FDA approved. The G6 is modeled after commercially available, FDA approved CGM devices. The differences between the G6 and commercially available devices are a reduced calibration scheme, meaning less finger stick blood glucose measurements for calibration; a longer wear for up to 10 days for the G6 vs. 7 days for commercially available product. Last, commercially available devices could give false high glucose readings if individuals took acetaminophen. The G6 sensor contains updated sensor technology aimed to block the interference of acetaminophen.

After randomization into placebo or metformin groups, the pre-diabetic subjects will begin a 12-wk exercise

intervention consisting of 3 days per week of aerobic exercise training with post-exercise consumption of a 20 gram protein beverage or isocaloric carbohydrate beverage. We have completed this supplementation protocol in previous studies and a currently ongoing investigation.

At the 8-wk time point, pre-diabetic subjects will begin the daily consumption of heavy water (D2O) for the assessment of mitochondrial and individual protein synthesis. At the completion of the training period, the pre-diabetic subjects will repeat all assessments performed prior to training including the DEXA, VO2max, OGTT and muscle sample. Muscle samples obtained pre- and post-training will be used to evaluate mitochondrial function using high-resolution respirometry, western blot analysis, and stable isotope incorporation (post only).

Healthy participants will complete the medical history questionnaire, resting ECG, graded exercise testing (ECG and VO2max), DEXA, OGTT, CGM, and muscle biopsy.

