**Identify exclusion criteria.**

Medications contraindicated with Metformin (Dofetilide, Lamotrigine, Pegvisomant, Somatropin, Trimethoprim, Trospium, Gatifloxacin, Cephalexin, Cimetidine, Dalfampridine)  
Recent (less than 6 weeks) or planned imaging that requires IV contrast  
Renal failure, creatinine  $\geq$  1.3 mg/dL in men or  $\geq$  1.2 mg/dL in women  
ALT levels exceed 52 IU/L  
Heart, Kidney or Liver Disease  
Type I or Type II Diabetes  
Anti-coagulant therapy (warfarin/heparin)  
Lung/respiratory dysfunction  
Medications affecting primary outcomes  
Lactose Intolerant  
Tobacco Use  
Heavy Alcohol Use  
Cancer  
Lidocaine Allergy  
EKG that is nondiagnostic for ischemia, such as: Complete Left bundle branch block or nonspecific Intraventricular conduction delay with ST/T changes; LVH with significant ST changes; Wolff-Parkison-White syndrome; ventricular pacemaker; digoxin therapy with greater than 1 mm ST depression or  
Arrhythmias, such as: Uncontrolled rate in atrial fibrillation; nonsustained ventricular tachycardia.

- i) **Describe your screening procedures. Attach your screening document(s) (e.g., health history questionnaire) in the Attachment Section (#16).**

Blood draw for chemistry panel, health questionnaire, medical history questionnaire, oral glucose tolerance test, resting and exercise EC.

- j) **Describe how you will be cognizant of other protocols in which subjects might be participating. Please explain if subjects will be participating in more than one study.**

Subjects will be instructed to communicate with investigators should they consider or begin to participate in other studies. Subjects participating in studies that may confound the results of the present investigation will be asked to withdraw from the the present investigation.

- k) **Compensation. Explain the amount and schedule of compensation, if any, that will be paid for participation in the study. Compensation includes food, gift cards, money, tokens, etc. Include provisions for prorating payment, if applicable. Compensation should be prorated if several activities are involved for different time periods (e.g., \$10 for session #1, and \$10 for session #2).**

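### No primary outcome or contrast is named, P<0.05 is applied without error control across outcomes or change-score t-tests, and an exclusion relies on undefined primary outcomes

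*Combined protocol and SAP*

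**What the plan says.** The Statistical Plan is a single paragraph. It states that "a significance was set a priori at" P<0.05 and describes a Treatment Group by Time ANOVA with repeated measures on time. It then says: "Upon a significant effect, a Holm-Sidak's post-hoc test was used for multiple comparisons". For pre-to-post change between groups, "data were analyzed using an unpaired t-test". Pearson's r "was used to determine associations between dependent variables". It lists no outcomes, ranks none, and does not say which arms each t-test compares.

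Purpose of the study (item 1a) proposes that "post-exercise milk protein feeding will enhance the mitochondrial protein synthesis (biogenesis) response to an exercise-training program", and then that feeding will overcome a possible blunting effect of metformin. It does not call either outcome primary. Study Procedures (item 2a) sets out four arms and says that after training participants "repeat all assessments performed prior to training including the DEXA, VO2max, OGTT and muscle sample". The same section lists respirometry, western blots and isotope incorporation on the muscle samples, the last of these measured after training only.

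Two places depend on a primary outcome being known. The Study Overview screens out people on "medications known to affect the primary outcomes", and the exclusion criteria (item 8h) list "Medications affecting primary outcomes". Neither says what those outcomes are.

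**The concern.** With four arms, many measured outcomes and one per-test threshold, the plan does not say which result would count as the trial's answer. A significant difference on any outcome, between any pair of arms, could be presented as showing that milk protein works or that it counters metformin. Item 1b looks for first-of-its-kind evidence on the former and a demonstration of the latter, so the error rate bears directly on the conclusions the sponsor hopes to draw.

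The undefined term also matters for eligibility. Drugs relevant to aerobic capacity, to glucose handling and to muscle mitochondria need not be the same, so the supplied text does not tell a screener what the criterion covers.

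**Working it through.** The documents state no family-wise error rate, power or sample-size calculation, so there is no planned figure to reproduce. The calculation below is illustrative.

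**Inputs from the documents**
- Threshold 0.05 per test (Statistical Plan). Sidedness is not stated; two-sided is assumed.
- Four arms (item 2a), hence 4 × 3 / 2 = 6 pairs.
- 60 planned completers (item 8a), so 60 / 4 = 15 per arm if allocation is equal. The ratio is not stated.

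**Assumed inputs**
- Outcome count. The measurements described give about 11: mitochondrial protein synthesis, respirometry, western blots, VO2max, OGTT glucose, OGTT hormones, four DEXA measures (percent fat, lean mass, adipose mass, bone density) and continuous glucose monitoring (CGM). The plan does not say that all are tested.
- A common correlation between test statistics, varied from 0 to 0.9.

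**Step 1: one test per outcome, independent.** The chance of at least one false positive is 1 − 0.95^k.
- k = 11: 1 − 0.95^11 = 1 − 0.569 = 43.1%
- k = 10 (without the optional CGM sub-study): 40.1%
- k = 8 (the four DEXA measures counted as one): 33.7%
- k = 6: 26.5%

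**Step 2: one test per outcome, correlated.** Simulation of equicorrelated two-sided z-tests, 400,000 runs:

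| Correlation | k = 11 | k = 6 |
|---|---|---|
| 0.3 | 37.5% | 24.2% |
| 0.5 | 30.3% | 20.7% |
| 0.7 | 22.3% | 16.3% |
| 0.9 | 13.2% | 10.8% |

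**Step 3: the change-score t-tests.** Six unadjusted unpaired t-tests among four arms of 15, on one outcome with no true differences (200,000 runs), give at least one false positive in 20.5% of runs. Accepting a significant group F-test on change or any of the t-tests gives the same 20.5%. If comparisons are read only after a significant F-test, the figure is 5.0%. The ANOVA gate therefore protects only if the t-tests sit behind it, and the plan does not say that they do. With the six t-tests run on each of two independent outcomes, the rate is 1 − (1 − 0.205)^2, about 37%; on four, about 60%.

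**Step 4: after a fix.** One outcome with one contrast at 0.05 gives 5.0%. For comparison, Bonferroni over 11 outcomes uses 0.05 / 11 = 0.0045 each, and 1 − (1 − 0.0045)^11 is about 4.9% under independence.

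**Step 5: can the planned tests analyse the hypothesised outcome?** Isotope incorporation is measured only after training. A Group by Time ANOVA needs two time points and a change-score t-test needs a pre value. Neither applies, so the outcome in the item 1a hypothesis has no between-group test in the Statistical Plan.

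**The case against.** The strongest reply has four parts.

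- **The percentages are not properties of the plan.** This stands. The documents give neither an outcome count nor correlations. Several DEXA readouts are linked by construction, and CGM is an optional sub-study with 20 prediabetic participants and its own aims. A reader might infer that the plan carries a 43% false-claim rate; the documents do not support that as a fixed figure. But six outcomes at a correlation of 0.9 still give 10.8%, over twice the nominal level, so the conclusion does not depend on the exact count.
- **Holm-Sidak already handles multiplicity.** It does so among comparisons within one outcome's ANOVA. It does not reach other outcomes, and nothing ties the change-score t-tests to it.
- **A primary outcome may be defined elsewhere.** A reader might infer that the trial has none at all. The documents do not support that: the Attachments section lists a GCP protocol whose text is not supplied and which could define one. Item 1a also makes mitochondrial protein synthesis the natural lead. What can be said is that the supplied text designates none.
- **The exclusion may work in practice.** Attached screening forms, also not supplied, may list drugs. Nothing supplied shows that the criterion was applied inconsistently, and that should not be claimed.

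**Conclusion.** The point holds in this form. The supplied documents designate no primary outcome and no primary contrast. P<0.05 is applied without control across outcomes or across the change-score t-tests, and two eligibility statements rest on primary outcomes that are not defined there.

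Under the assumption of 11 outcomes tested once each, the chance of at least one false positive runs from about 13% (correlation 0.9) to about 43% (independence). This is not an upper bound: a single outcome reaches about 20% if all six pairs of arms are compared by unadjusted t-tests, assuming 15 per arm.

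The Statistical Plan is written in the past tense, and a reader might infer that outcomes were chosen after the results were known. The documents do not show this; they leave open whether outcome data had been seen by group.

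**What to change.** - **Primary outcome and contrast.** Name mitochondrial protein synthesis from the post-training biopsy as the single primary outcome, with protein versus carbohydrate as the single primary contrast at two-sided 0.05. Analyse the post-training value between groups, for example by a protein × metformin two-way ANOVA, because there is no pre value.
- **Everything else.** Label the other outcomes, the change-score t-tests and the correlations as secondary or exploratory, and report estimates with 95% confidence intervals. If further claims are wanted, put them in a fixed order, each tested only if the one before is significant. VO2max followed by one named OGTT summary is one possibility. Each step needs one named contrast, and so does any claim that feeding opposes metformin.
- **Eligibility wording.** Make the Study Overview and the exclusion criteria refer to the named outcomes. If the GCP protocol already defines the primary outcomes, cite it in both places and in the Statistical Plan, and align the hierarchy with it.
- **Timing.** If outcome data have already been seen by group, date the hierarchy and label it post hoc.

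The cost is wording in the Statistical Plan and the eligibility sections, an added analysis for the post-only outcome, and fewer outcomes on which significance can be claimed.

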**b) What does the Investigator(s) hope to learn from the study?**

We hope to:

- a) provide the first evidence that post-exercise milk protein supplementation is effective in diseased population (i.e., older adults with pre-diabetes) and those on medications (i.e., metformin).
- b) demonstrate that the potential inhibitory effects of metformin on aerobic exercise adaptations can be opposed by milk protein feeding.

Sub-study

1. Glucose Profiles via CGM in pre diabetic individuals before, during and after the intervention (i.e., aerobic exercise training with or without metformin with post-exercise carbohydrate or carbohydrate+protein feeding as listed below in 2a).
- 2: Glucose profiles via CGM in healthy individuals. Healthy individuals will complete baseline procedures but will not complete an intervention.

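### The trial crosses drink with drug, but the plan analyses one undefined group factor, has no drink-by-drug term, and states no between-group test that fits post-only protein synthesis

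*Combined protocol and SAP*

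**What the plan says.** The Study Overview in section 2(a) assigns participants to "exercise + carbohydrate + placebo, exercise + protein + placebo, exercise + carbohydrate + metformin, or exercise + protein + metformin". That is a complete 2x2 of drink by drug.

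The purpose has two parts. Section 1(a) proposes that "post-exercise milk protein feeding will enhance the mitochondrial protein synthesis (biogenesis) response to an exercise-training program" (aim 1 below) and that "this stimulatory effect of protein feeding will overcome the potential blunting effect of metformin on exercise responses" (aim 2). Section 1(b) restates the second as a hope to "demonstrate that the potential inhibitory effects of metformin on aerobic exercise adaptations can be opposed by milk protein feeding".

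The Statistical Plan is one paragraph. Its main model is "A two-way ANOVA (Treatment Group x Time) with repeated measures for time was performed". It continues: "Upon a significant effect, a Holm-Sidak's post-hoc test was used for multiple comparisons". Change is compared "from pre to post-intervention between groups, data were analyzed using an unpaired t-test", with no adjustment stated. Pearson correlation is the only other test of outcomes, at a significance level of 0.05. The paragraph does not say which arms make up the group factor, which groups enter the t-test, or which test serves which aim.

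On the outcome named in aim 1, the Study Overview has participants begin "daily consumption of heavy water (D2O) for the assessment of mitochondrial and individual protein synthesis" at week 8 of 12, and marks stable isotope incorporation as measured after training only. Respirometry and western blot are done on both the pre- and post-training samples.

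**The concern.** A 2x2 trial gets its efficiency from comparing all protein with all carbohydrate participants, and it is the natural design for asking whether one factor changes the effect of the other. The written analysis uses neither feature. It contains no drink factor, no drug factor and no drink-by-drug term. A t-test compares two groups, and the trial has four.

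Three things are at stake. If the factor has four levels, the overall protein effect is reached only through an omnibus test and pairwise follow-up, which costs power. If arms are pooled over drug, the question about metformin is not addressed. And the isotope measure, which bears directly on aim 1, has no pre value to put into a Group x Time model or a change score.

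**Working it through.** **The plan's own number.** The documents give no effect size, SD, power or allocation ratio, so no power figure can be reproduced. The only sample-size figure is 60 completers (section 8(a)). It follows from 120 recruits with both upper losses taken off the same base: 120 x (1 - 0.25 - 0.25) = 60. Taken in sequence, the losses give 120 x 0.75 x 0.75 = 67.5 to 120 x 0.85 x 0.85 = 86.7.

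**Assumptions.** Equal arms, so 60/4 = 15 per arm (up to about 22 on the sequential reading); two-sided 0.05; effects in SDs of change; error df = 4 x 15 - 4 = 56. With two time points, Group x Time is equivalent to a one-way ANOVA on change. The figures show scale only.

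**Standard errors in SD units.**
- Marginal protein effect (30 v 30): sqrt(2/30) = 0.258
- Protein within one drug stratum (15 v 15): sqrt(2/15) = 0.365
- Interaction, a difference of differences: sqrt(4/15) = 0.516

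**Overall protein effect, 0.736 SD in both drug strata.** This size is chosen because it gives the marginal contrast 80% power.
- Marginal 1-df contrast, noncentral t, 0.736/0.258 = 2.85: 80%
- Four-level omnibus, noncentral F(3, 56), noncentrality 15 x 4 x 0.368² = 8.13: 63%
- Step-down Holm-Sidak over six pairs after a significant omnibus (simulated): 27% for one given within-stratum pair, 44% for at least one of the two
- The same single pair as one unadjusted contrast: 51%

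The fall from 80% to 51% is therefore sample size (30 v 30 against 15 v 15). The further fall to 27% comes from the gate and the adjustment. At 22 per arm the marginal, omnibus and at-least-one figures are 93%, 82% and 66%.

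**Protein within metformin, 1.0 SD there and none under placebo.**
- 1-df contrast, 56 df: 77%
- Holm-Sidak after a significant omnibus: 54%
- The plan's unpaired t-test on change, 28 df: 75%
- Interaction contrast: 48%

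At 22 per arm the first three are 91%, 76% and 90%. If the unadjusted t-test is run on all six pairs at 15 per arm with no true differences, the simulated family-wise error is 20% (1 - 0.95^6 = 26% if the tests were independent).

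**Two levels pooled over drug.** A 30 v 30 t-test of drink has 80% power at 0.736 SD, and 78% or 73% if metformin blunts the response by 0.5 or 1.0 SD, because the drug effect then enters the error. Drug is not in this comparison, so it tests neither protein within metformin nor the interaction.

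**Interaction.** Effect needed for 80% power: 2 x 0.736 = 1.47 SD. 95% CI half-width: 2.003 x 0.516 = 1.03 SD.

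**Isotope outcome.** Group x Time needs two times and the t-test is stated for change. One post-training value supplies neither, and a correlation does not compare groups. This holds however the group factor is defined.

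**The case against.** The strongest reply is that the plan already has a serviceable route to aim 2. The unpaired t-test on change carries no stated adjustment, and for protein v carbohydrate within metformin it has 75% power against 77% for the factorial contrast. That stands. A reader might set 77% beside 54% and infer that the plan sacrifices aim 2. The loss arises only on the Holm-Sidak route. On the t-test route the exposure is to error inflation across pairs.

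A reader might also infer that aim 2 has no test at all. The documents do not support this. It is true if the levels are pooled over drug, but two levels could equally be the two drinks within the metformin arms, and four levels include that pair. Which reading applies cannot be determined.

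Nor is a four-level factor invalid: its group-by-time test contains the 2x2 contrasts. What it lacks is a direct test of them.

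It is also fair to say that the aims do not fix the aim 2 contrast. Overcoming or opposing blunting could mean a protein effect within metformin or an interaction. The first alone cannot separate opposing metformin from helping everyone, and neither shows that blunting occurred.

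The isotope gap is narrow, since respirometry and western blot have pre and post values. No outcome is formally labelled primary. The attachments list grant papers and a separate GCP protocol that were not supplied and may say more.

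**Conclusion.** The point holds as a gap between design and analysis, limited to the supplied text. The plan has no drink or drug factor, never tests their interaction, links no test to an aim, and states no between-group test that fits the isotope measure of protein synthesis. These parts need no power assumption.

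The size of the efficiency loss is conditional on equal arms, 15 per arm and an assumed 0.736 SD. On a four-level reading, the overall protein effect goes from 80% power as one contrast to 63% for the omnibus and 44% for at least one within-stratum pair. On a reading pooled over drug, the drink effect keeps most of its power and the metformin question is lost. For protein within metformin, the cost is either power (54%) or about 20% family-wise error over six pairs, depending on the route taken.

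A reader might go further and infer that the plan would take one significant and one non-significant drug stratum as proof of effect modification. Nothing in it prescribes that. This should be fixed, but the text does not show the analysis to be invalid.

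**What to change.** In the Statistical Plan, replace the single group factor with two factors, drink and drug. Fit 1-df contrasts for protein, metformin and protein x metformin on the change or the baseline-adjusted post value, and on the post value alone for isotope-based protein synthesis. Then:

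- Use the marginal protein effect for aim 1.
- Have the investigators name the aim 2 contrast: protein within metformin, or the interaction. In either case also report metformin v placebo within carbohydrate, so that blunting is shown and not presumed.
- State the alpha for each aim: 0.05 each without joint control, or 0.025 each. At 0.025 and 15 per arm, power is 71% for the marginal effect at 0.736 SD and 67% for protein within metformin at 1.0 SD.
- Report the interaction as an estimate with its 95% CI, acknowledge the limited precision shown above, and do not infer it from differing p-values.
- Replace the unspecified t-test on change with these contrasts, and give the four arm means.

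The cost is a different model on the same data, with some pairwise comparisons becoming secondary. The plan is written in the past tense, so this may mean re-analysis. Any contrast chosen after results were seen must be labelled as such.

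### Pre-to-post change is compared between groups by an unpaired t-test without baseline as a covariate; a baseline-adjusted model would be more precise at almost no cost

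*Combined protocol and SAP*

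**What the plan says.** The Statistical Plan is one paragraph in the past tense. Its main model is a two-way ANOVA of treatment group by time, with time as the repeated factor. It continues: "Upon a significant effect, a Holm-Sidak's post-hoc test was used for multiple comparisons". A separate sentence then deals with change: "from pre to post-intervention between groups, data were analyzed using an unpaired t-test". No covariate appears in either analysis. The change sentence does not say which groups are compared or whether these t-tests are adjusted for multiplicity.

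Protocol section 2(a), Study Overview, randomises to four arms: "exercise + carbohydrate + placebo, exercise + protein + placebo, exercise + carbohydrate + metformin, or exercise + protein + metformin". It adds: "Subjects who meet these criteria will be randomized so that subject characteristics are matched between groups". It does not name the characteristics or the method. The same section says that after training the pre-diabetic participants will "repeat all assessments performed prior to training including the DEXA, VO2max, OGTT and muscle sample". Baseline values of these outcomes are therefore collected. The stable-isotope outcome is measured only after training.

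The purpose (section 1a) describes the study as "in older adults with pre-diabetes with or without metformin treatment". One aim in section 1b is to "demonstrate that the potential inhibitory effects of metformin on aerobic exercise adaptations can be opposed by milk protein feeding". Section 8a plans for 60 completers.

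**The concern.** A t-test on change subtracts the whole of the baseline value, which amounts to fixing the slope of post on baseline at 1. With equal SDs the best-fitting slope is the pre-post correlation r, which is below 1. Two things follow. The contrast has more variance than it needs. An arm that happens to start higher will also tend to show a smaller change, and the t-test leaves that in the estimate.

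The trial is small: about 15 completers per arm if allocation is equal. The data needed to recover the lost precision are already collected, so the loss is avoidable.

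**Working it through.** The plan gives no power, SD, effect size or correlation, so there is no figure of its own to reproduce.

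**Inputs from the documents.** 60 planned completers (section 8a); four arms (section 2a); significance at 0.05 (Statistical Plan).

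**Assumptions.** Equal allocation, so 60/4 = 15 per arm, or 30 v 30 when one factor is pooled over the other; two-sided testing; equal SDs before and after; r = 0.5, 0.7 or 0.9.

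**1. Variance.** In units of the baseline variance, a change score has variance 2(1 - r). The ANCOVA residual has variance 1 - r². The ratio is (1 - r²) / [2(1 - r)] = (1 + r)/2.

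| r | change score | ANCOVA | ratio |
|---|---|---|---|
| 0.5 | 1.00 | 0.75 | 0.75 |
| 0.7 | 0.60 | 0.51 | 0.85 |
| 0.9 | 0.20 | 0.19 | 0.95 |

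In 20,000 simulated trials at each r (four arms of 15; protein versus carbohydrate within metformin) the ratios were 0.761, 0.870 and 0.969. They are slightly higher because the slope has to be estimated.

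**2. Width of the 95% CI.** The square roots of the ratios are 0.866, 0.922 and 0.975, so the limiting gains are 13.4%, 7.8% and 2.5%. For one arm pair, 15 v 15, the mean half-widths in SDs of change are:

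| analysis | error df | r = 0.5 | r = 0.7 | r = 0.9 |
|---|---|---|---|---|
| t-test, two arms | 28 | 0.741 | 0.742 | 0.742 |
| change score, error pooled over four arms | 56 | 0.728 | 0.728 | 0.728 |
| four-arm ANCOVA | 55 | 0.637 | 0.678 | 0.717 |

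From the first row to the third the interval narrows by 14%, 9% and 3%. Part of that is pooling: 1 - 0.728/0.741 = 1.8%. The part due to baseline alone compares the second row with the third:

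- r = 0.5: 1 - 0.637/0.728 = 12.5%
- r = 0.7: 1 - 0.678/0.728 = 6.9%
- r = 0.9: 1 - 0.717/0.728 = 1.5%

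That is about 13%, 7% and 2%. The approximate gain for a pooled 30 v 30 contrast is the same.

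**3. Power.** The smallest difference with 80% power by t-test is 1.06 SD of change at 15 v 15 and 0.74 at 30 v 30. With baseline adjusted, the same effect has power of about 90%, 86% and 82% at the three correlations (ignoring the small cost of estimating the slope).

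**4. Chance imbalance.** Without effective matching on baseline, the SD of the baseline difference between two arms is √(2/15) = 0.365 baseline SD. A difference of that size moves the change contrast by (1 - r) x 0.365 / √[2(1 - r)], which is 0.18, 0.14 and 0.08 SD of change.

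**5. Overlap with the ANOVA.** With two time points, the Group x Time test is an analysis of the change scores. If it uses the same two groups as the t-test, then F = t². It therefore lacks baseline adjustment in the same way.

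**The case against.** **The t-test is valid, so this is only a preference.** The first half stands. Under randomisation the change-score comparison is unbiased, and a reader who infers systematic bias from the missing covariate goes too far. What remains is a loss of precision. Its size depends on a correlation that the documents do not give, and near 0.9 it is small.

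**Matching already handles baseline.** It may reduce imbalance. But the protocol does not say that outcome baselines are among the matched characteristics, and the stated analysis adjusts for none of them.

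**Changing the model after the data are in adds discretion.** This is fair. The plan is written in the past tense, so the new model must be labelled as later and shown with the stated test.

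**A stronger reading about error rates.** A reader might infer that the plan runs several unadjusted t-tests across four arms. For unadjusted tests without blocking, simulated familywise error per outcome would be 16% for the four pairs that differ in one factor and 20% for all six pairs. The documents do not establish this. An unpaired t-test takes two groups, and section 1a also allows a single contrast of with versus without metformin, for which the error is 5%. If the matching factors are prognostic, the multi-pair figures fall too, to 3% (four pairs) and 4% (six) with full blocking and an assumed R² of 0.5. Nor does the plan lack a multiplicity method: it names Holm-Sidak, though not for these t-tests. The unnamed groups are a missing detail, not a demonstrated error.

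**Conclusion.** The point holds as a question of efficiency. The stated test is valid but less precise than a baseline-adjusted model built on values the trial already collects, and it leaves chance baseline differences in the estimate. The ANCOVA variance is 75%, 85% or 95% of the change-score variance at r = 0.5, 0.7 or 0.9. The interval narrows by about 13%, 7% or 2% from baseline alone; for an arm pair, pooling error over four arms adds about 2 points.

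These figures rest on the assumed correlations, equal SDs before and after, and equal allocation of 60 completers. Neither bias nor inflated type I error is shown. The gain is modest but nearly free, so the change is worth making.

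**What to change.** For each outcome with pre and post values:

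- Fit one ANCOVA: post value on baseline value, protein, metformin and protein x metformin.
- Make it the governing between-group analysis, in place of both the change-score t-test and the between-group Group x Time test. Keep the ANOVA for within-group time effects only. Otherwise two tests of the same hypothesis could disagree with no rule for which one counts.
- Report adjusted differences with 95% CIs and state which comparison was meant. Average a metformin or protein main contrast over the levels of the other factor; with reference coding and the interaction in the model, the metformin coefficient alone is the effect under carbohydrate only.
- If several arm pairs are reported, name them, take them from this model and apply the Holm-Sidak method that the plan already names.
- Label the model as specified after data collection and show the plan's t-test beside it.

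The post-only isotope outcomes are unaffected.

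**Cost.** Wording, a re-run on existing data and one degree of freedom for baseline. The gain is small if r is near 0.9. If four pairs are put under Holm-Sidak, the first step needs P < 0.0127. The difference detectable there with 80% power is 1.10, 1.17 or 1.23 SD of change at r = 0.5, 0.7 or 0.9, against 1.06 for one unadjusted t-test, so some results below 0.05 may no longer count. A model chosen after data collection is also weaker evidence than a pre-specified one.
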